#### 4.2.3 Secondary Endpoint #1 (All-cause hospital admission, ED visit with HK, all-cause death, rescue therapy for HK)

*Time to first occurrence of any component of all-cause hospital admission or ED visits with HK as a contributing factor, or all-cause death, or use of rescue therapy for HK at any time post-discharge up to 180 days.*

##### 4.2.3.1 Definition

- Population: Full analysis set
- Endpoint: Time to first occurrence of either component of the composite outcome at any time post-discharge up to 180 days.
- Intercurrent event strategy: Participants who discontinue of treatment will continue to be followed up to the first component of the composite endpoint (treatment policy strategy). Rescue therapy for HK will be considered an event (composite variable strategy). Participants who require ED visits without HK as a contributing factor will continue to be followed up to the first component of the composite endpoint (treatment policy strategy). Participants who die of any cause will be considered an event

(composite variable strategy). Participants who are lost to follow-up will be censored at the date of loss to follow-up. Participants who have RAASi down-titration (including discontinuation) will continue to be followed up to the first component of the composite endpoint (treatment policy strategy).

- Population level summary (analysis): Kaplan-Meier plots of the survival function for the SZC and SoC treatment groups will be presented. Log-rank test for testing will be used to calculate a two-sided p-value, Cox proportional hazards ratio for estimation, with randomised treatment group (reference level SoC) as the independent variable. The HR and the two-sided 95% confidence interval will be presented. The Risk Difference (RD) and two-sided 95% confidence interval will be presented at 180 days post-discharge.

#### **4.2.3.2 Derivations**

Time to first occurrence will be defined as the earliest date of (all-cause hospital admission, ED visits with HK as a contributing factor, all-cause death, use of rescue therapy for HK, date of loss to follow-up, date of 180 days post-discharge) – date of randomization + 1.

Risk Difference (RD) is calculated using the Austin method (Austin et al; 2010). First, the predicted probability of survival for each participant at 180 days post-discharge is calculated assuming that all participants do not receive SZC (Cmean). Second, the predicted probability of survival for each participant at 180 days post-discharge is calculated assuming that all participants receive SZC (Tmean). The RD is calculated as Tmean-Cmean. The 95% confidence interval will be calculated by taking the 2.5th and 97.5th percentiles of RDs across 1000 bootstrap samples where each bootstrap sample is drawn randomly with replacement from the original sample, such that the new sample is of the same size as the original sample.

#### **4.2.3.3 Handling of Dropouts and Missing Data**

Participants who are lost to follow-up will be censored at the date of discontinuation as recorded on the participant's disposition form.

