4.4 End of Study Definition

A participant is considered to have completed the study if he/she has completed all phases of the study including the last scheduled procedure at visit 11, as shown in the Schedule of Activities (SoA; [Table 1](#)).

The end of the study is defined as the date of the last scheduled procedure shown in the SoA for the last participant in the study.

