7.3 Lost to Follow-up

A participant will be considered lost to follow-up if he or she repeatedly fails to return for scheduled visits and no contact has been established by the time the study is completed (see [Section 4.4](#)), such that there is insufficient information to determine the participant's status at that time.

Participants who decline to continue participation in the study, including telephone contact, should be documented as ‘withdrawal of consent’ rather than ‘lost to follow-up’. Investigators should document attempts to re-establish contact with missing participants throughout the study period. If contact with a missing participant is re-established, the participant should not be considered lost to follow-up and evaluations should resume according to the protocol.

The following actions must be taken if a participant fails to return to the clinic or to answer a phone call for a required study visit:

- The site must attempt to contact the participant and reschedule the missed visit as soon as possible and counsel the participant on the importance of maintaining the assigned visit schedule and ascertain whether or not the participant wishes to and/or should continue in the study.
- Before a participant is deemed lost to follow-up, the investigator or designee must make every effort to regain contact with the participant (where possible, 3 telephone calls and, if necessary, a certified letter to the participant's last known mailing address or local

equivalent methods). These contact attempts should be documented in the participant's medical record.

Discontinuation of specific sites or of the study as a whole are handled as part of [Appendix A](#).

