#### **4.2.5.4 Primary Analysis of Secondary Endpoint #3**

A descriptive summary (Mean, SD, Median, Range) of the number of all-cause hospital admissions or ED visits with HK as a contributing factor will be presented by randomised treatment group in the FAS. A negative binomial regression model will be conducted with the number of all-cause hospital admissions or ED visits with HK as a contributing factor as the dependent variable and randomised treatment group (reference level SoC) as the independent variable. The duration of time per participant in study is calculated until the earliest of loss to follow-up or 180 days post-discharge and will be included in the model as an offset term. The incidence rate ratio (SZC/SoC), along with 95% CIs and two-sided p-values will be displayed.

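### The censoring date for loss to follow-up is a disposition-form date not tied to the last known event status, so unobserved time can be counted as event-free up to Day 180

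*SAP*

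**What the plan says.** The estimand in SAP 4.2.3.1 reads: "Participants who are lost to follow-up will be censored at the date of loss to follow-up". The derivation in SAP 4.2.3.2 takes the earliest of the event dates and "date of loss to follow-up, date of 180 days post-discharge". SAP 4.2.3.3 makes the rule operational: "Participants who are lost to follow-up will be censored at the date of discontinuation as recorded on the" participant's disposition form. The same sentence recurs for the other time-to-event endpoints, including secondary endpoints #2, #4 and #5 (SAP 4.2.4.3, 4.2.6.3, 4.2.7.3).

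For the count endpoints, SAP 4.2.5.4 measures time in study "until the earliest of loss to follow-up or 180 days" post-discharge and enters it as the offset. It does not mention the form and does not define the loss date.

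The only definition of loss is in Protocol 7.3. The participant repeatedly fails to return and "no contact has been established by the time the study is completed", with a reference to Section 4.4. The same section adds: "Before a participant is deemed lost to follow-up, the investigator or designee must make every effort to regain contact with the participant". No deadline is given for those attempts. Protocol 4.4 requires all phases for a participant to be complete, "including the last scheduled procedure at visit 11". For the trial as a whole it states: "The end of the study is defined as the date of the last scheduled procedure" for the last participant.

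**The concern.** Censoring is sound when follow-up ends on the last day on which an event would have been known. The form date need not be that day. It may be the day the site stopped trying, or the day the status was settled. Visit 11 comes about 7 days after the Day 180 visit, so a date set at completion normally falls beyond the cap.

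Take a participant last reached at the Day 30 call whose form is dated after Day 180. The derivation gives 180 days at risk with no event, although nothing is known about 180 − 30 = 150 of them.

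This pulls event probabilities down in each arm in proportion to its loss. If loss differs between arms, which is plausible in an open-label trial, the arm with more loss looks better. The endpoint affected is the one that sized the trial and stands second in the testing order. Sites could also enter different dates for identical cases.

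**Working it through.** **The plan's own figure.** Inputs from Protocol 9.2.2: event-free at 180 days 83% (SZC) and 56.8% (SoC), 5% significance level, 80% power. The SAP makes the test two-sided.
- HR = ln(0.83)/ln(0.568) = 0.329.
- Freedman events = (1.960 + 0.842)² × [(1 + 0.329)/(1 − 0.329)]² = 30.8, rounded up to 31.
- Per arm: 31/(0.17 + 0.432) = 51.5, so 52, or 104 in total.
- Drop-out: 104/0.8 = 130 randomised; 130/0.8 = 162.5, so 163 enrolled.

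The plan's figures reproduce, and the censoring date does not alter them.

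**Worst-case assumptions.** All of the 20% post-randomisation drop-out is loss to follow-up. Last contact is uniform over 0 to 180 days. The hazard is constant. The form date is after Day 180. No event is found after last contact.

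**Absolute risks, closed form.** Let p be the true 180-day risk, d the proportion lost and L = −ln(1 − p). When time runs to Day 180, the estimated risk is

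(1 − d)·p + d·[1 − (1 − e^(−L))/L].

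- SoC: L = 0.5656; bracket = 1 − 0.432/0.5656 = 0.236; risk = 0.8 × 0.432 + 0.2 × 0.236 = 0.393.
- SZC: L = 0.1863; bracket = 1 − 0.17/0.1863 = 0.088; risk = 0.8 × 0.17 + 0.2 × 0.088 = 0.154.
- Risk difference: 39.3 − 15.4 = 23.9 points, against 43.2 − 17.0 = 26.2.
- Implied HR: ln(0.846)/ln(0.607) = 0.334, against 0.329.

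Smaller equal losses do less. Event-free estimates are 57.8% (SoC) and 83.4% (SZC) at 5% loss, and 58.8% and 83.8% at 10%.

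**Test and hazard ratio, simulation** (65 per arm, 4,000 runs, exponential event times, two-sided 5% log-rank):

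| Loss SZC / SoC | Censored at | Median HR, planned effect | Power | False-positive rate, no effect |
|---|---|---|---|---|
| 20% / 20% | last contact | 0.33 | 88.7% | 4.8% |
| 20% / 20% | Day 180 | 0.33 | 88.9% | 5.5% |
| 30% / 10% | last contact | 0.33 | 88.6% | 5.1% |
| 30% / 10% | Day 180 | 0.29 | 94.4% | 6.9% |
| 10% / 30% | last contact | 0.33 | 89.0% | 5.0% |
| 10% / 30% | Day 180 | 0.37 | 79.8% | 8.0% |

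The simulation error of a rate near 7% is about √(0.07 × 0.93/4000) = 0.4 points. With no effect the last two Day 180 rows estimate the same quantity by symmetry, and a separate run of 30% against 10% gave 6.8%, so about 7% is a fair summary. With 30% lost on SZC and no true effect, 6.0% of trials reject in favour of SZC, against 2.4% when censoring at last contact, and the median HR is 0.89. Imbalances of 10 points (10% v 0%, 15% v 5%, 25% v 15%) gave 5.4% to 5.7% in 12,000 runs.

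**Count offset.** If the same late date is used, 20% loss with mean last contact at Day 90 gives a true mean observation time of 0.8 × 180 + 0.2 × 90 = 162 days, but 180 are counted. A constant event rate is then understated by the factor 162/180 = 0.90 in each arm. The rate ratio is unaffected if loss is equal.

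**The case against.** The stronger reading, which a reader might infer, is that every lost participant is dated at study completion and so always counted event-free to Day 180. The documents do not support that. Protocol 7.3 defines a status, not the date to be entered on the form, and the form is not described. It also speaks of deeming a participant lost after calls and a letter, so an earlier date is possible, and the entry could even be the last contact. Other sections treat loss as datable during follow-up. The primary-endpoint sensitivity analyses refer to loss before Day 180 and after Day 90 (SAP 4.2.2.5), and exploratory endpoint #17 to loss before Days 90 and 180 (SAP 4.2.25.1). Nor does SAP 4.2.5.4 say that the form date sets the offset.

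The size is also bounded. The 20% covers all drop-out, whereas Protocol 7.3 records those who decline to continue as withdrawals of consent, so 20% is an upper bound for true loss. Chart review (Protocol 8.8.1) may recover some admissions. The inverse-probability-weighted analysis (SAP 4.2.3.5) is fitted only to participants not lost, so it does not use the disputed date. With equal loss, the shrunken risk difference is conservative.

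All of this stands, and it limits the point without removing it. Even a date entered after calls and a letter is later than the last known event status, so the error runs in the same direction. Chart review depends on participant permission and sometimes on transferred records. The weighted analysis is only a sensitivity analysis. The reverse Kaplan-Meier plot planned to examine censoring (SAP 4.2.3.4) uses the same dates and would not reveal the problem.

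**Conclusion.** The point holds as a gap in a stated rule. The plan names a censoring date, does not tie it to knowledge of event status, and permits one late enough for the cap to turn silence into event-free follow-up. It is not shown that this will happen for every lost participant, or for most.

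Under the worst-case assumptions with equal loss, the harm is to the absolute risks (1.6 points too low on SZC, 3.9 on SoC) and to the risk difference (2.3 points too small), all pre-specified outputs. The test is essentially intact. Distortion of the test needs a large imbalance: 20 points moves the hazard ratio from 0.33 to between 0.29 and 0.37 and the false-positive rate to about 7%. More extreme splits, such as 40% against 10%, average 25% and exceed the planned total drop-out, so they should not be used to size the problem.

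The change should be made because the better rule is clear and cheap. Confidence is moderate, since the date actually recorded on the form is unknown.

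**What to change.** In SAP 4.2.3.3 and its repeats, define the censoring date as the last date on which event status was known: the latest completed visit, telephone contact or chart review, capped at Day 180. Use the same date in SAP 4.2.3.2 and the parallel derivations.

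Apply it to withdrawal of consent as well. Protocol 7.3 separates withdrawal from loss, and the time derivations list no withdrawal date. Read literally, a withdrawn participant has no censoring date before Day 180.

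Use the same date to end time in study for the count-model offset (SAP 4.2.5.4, which also governs secondary endpoint #6, and SAP 4.2.14.4 and 4.2.17.4).

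The cost is a few sentences in the SAP and a derived variable. Contacts are already scheduled at Days 7, 30, 60, 90, 120, 150 and 180, and the SAP already uses last contact to end the outpatient period (3.3.1.2). The sample size does not change.

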#### **4.2.3.4 Primary Analysis of Secondary Endpoint #1**

The primary analysis for the main secondary endpoint will be conducted using a log-rank test by treatment group in the FAS to calculate a two-sided p-value. A Cox proportional hazards model will be used in the FAS for estimation with randomised treatment group (reference level SoC) and subject recruitment country as the independent variables. Kaplan-Meier survival curves (product-limit estimates) of time to first event will be presented by treatment group, together with a summary of associated statistics (median time to failure and 95% CI). The proportion of participants event free at 90 day intervals (90, 180) will be summarised by treatment group. The summary at 90 days will be descriptive as the primary analysis is focused on 180 days. The median (range) duration of follow-up in censored participants will also be calculated.

To assess for the proportionality of hazards the log(-log(estimated survival function)) will be plotted compared to log(days) for each randomised treatment group and visually inspected to determine if the curves are approximately parallel. To assess for the impact of censoring, and the duration of follow-up, a reverse Kaplan-Meier figure will be produced where the status indicators are reversed such that the censor becomes the event and the composite event of interest as the censor. These will be presented by randomised treatment group, together with a summary of associated statistics (median time and associated 95% Cis).

#### **4.2.3.5 Sensitivity Analyses of the Secondary Endpoint #1**

Providing there are sufficient events within each covariate ( $> 10$  events) to support the analysis, the analyses of time-to-event secondary endpoints will be repeated in the FAS using an alternative population level summary where the Cox proportional hazards model will include randomised treatment group and the following baseline variables: age (as a cubic spline), sex (female, male), participant recruitment country, presence of heart failure (yes/no), diabetes (yes/no), RAASi use (yes/no), CKD stage and baseline  $K^+$  ( $5.0 < K^+ \leq 5.5$  versus  $5.5 < K^+ \leq 6.5$  mmol/L) as independent variables.

Additionally, the analysis will be repeated with the PPS analysis population.

Furthermore, a supplementary analysis will be conducted where participants who down-titrated (or discontinue) RAASi will be censored at the date of down-titration.

An additional sensitivity analysis will be conducted where participants who are lost to follow-up will be accounted for using an inverse probability weighting (IPW) approach where similar participants who were not lost to follow-up will be re-weighted (hypothetical strategy). First, a logistic regression model will be performed where the dependent variable is a binary indicator variable where 1 indicates not lost to follow-up and 0 indicates lost to follow-up. Randomised treatment group and the following baseline variables: age (as a cubic spline), sex, participant recruitment country, presence of heart failure, diabetes, RAASi use, CKD stage and baseline  $K^+$  ( $5.0 < K^+ \leq 5.5$  versus  $5.5 < K^+ \leq 6.5$  mmol/L) will be included as independent variables. The predicted values from this model will be calculated and the reciprocal of these will be the IPW. The Cox proportional hazards model will then be conducted on participants not lost to follow-up, following the intercurrent event strategy in section 4.2.3.1, where participants will be reweighted using the IPW.

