4 STUDY DESIGN

4.1 Overall Design

- This is a Phase 4, randomised, controlled, open-label, parallel-group, multicentre study in participants with CKD treated for HK whilst in hospital.
- Participants from 30 to 50 sites in 4 to 7 countries will be screened for enrolment. Assuming a 20% drop out rate from enrolment to randomisation and a 20% drop out post-discharge (post-randomisation), approximately 163 participants will have to be enrolled to achieve 104 evaluable participants (52 per arm). In total, up to a maximum of 163 participants will be enrolled, resulting in approximately 130 participants discharged and randomised and 104 evaluable participants (52 per arm).
- The study plans to enrol approximately equal numbers of participants with mild HK (K^+ between > 5.0 and ≤ 5.5 mmol/L) and with moderate/severe HK (K^+ between > 5.5 and ≤ 6.5 mmol/L), with a minimum of 30% of the enrolled participants in either group.
- During the in-hospital phase, participants will be treated with SZC as per local label (correction and/or maintenance treatment, see Section 6.1), starting at baseline and based on local K^+ measurement obtained within 24 hours of treatment initiation:
 - Participants with HK (K^+ between > 5.0 and ≤ 6.5 mmol/L): 1) stop current K-binder if any, 2) start SZC correction dose (note: participants currently on SZC should continue SZC correction dose, up to 72 hours).
 - Participants currently receiving any treatment for the current episode of HK and are already NK at baseline ($K^+ \leq 5.0$ mmol/L): 1) stop any current K-binder, 2) start SZC maintenance dose (note: participants currently on SZC maintenance dose should continue SZC maintenance dose).
 - All treatment decisions, including modification of the ongoing therapy for HK, must be based on the investigator's medical judgement of the participant's best interest.
- At discharge, NK participants who have been treated with SZC for between 1 and 21 days whilst in hospital and are started on SZC maintenance dose will be randomised in a 1:1 ratio to one of the following arms:
 - Arm A: Participants discharged with SZC, as per local label, to manage HK until the end of the outpatient phase
 - Arm B: Participants discharged with SoC, as per local practice, to manage HK until the end of study.

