9.2.2 Main Secondary Endpoint

Prior data: Based on assumptions over a 6-month period of 16.2% all-cause hospitalisation for SZC arm ([Pollack et al, 2023](#)) and 40% for SoC arm ([Thomsen et al; 2017](#), [Kanda et al; 2020](#), [Horne et al; 2019](#)), 0.8% ED visits with HK as a contributing factor in the SZC arm ([Pollack et al; 2023](#)) and 3.2% for SoC ([Tafesse et al; 2020](#), [Kashihara et al; 2019](#), [Kanda et al; 2020](#)), it is assumed that 17% and 43.2% of patients in the SZC and SoC arm will experience an event respectively.

Sample size estimate:

- Log-Rank Test for Equality of Survival Curves
- Significance level: 5%
- Power: 80%
- Hazard ratio (HR; SZC/SoC): 0.329
- Proportions without the main secondary composite outcome (event-free) at 180 days post-discharge:
 - Arm A (SZC): 83% (17% with the outcome/event of interest)
 - Arm B (SoC): 56.8% (43.2% with the outcome/event of interest).

The above test specifics and assumptions yield a sample size of 52 evaluable participants per arm (total N = 104). Assuming a 20% drop-out rate from enrolment to randomisation, and a 20% drop out post-randomisation, a total of approximately 163 participants will be enrolled.

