9.4.3.2 Secondary Endpoints

For each secondary endpoint, sensitivity analysis will be conducted including an analysis using the PPS population.

1. Time to first occurrence of any component of all-cause hospital admission, or ED visits with HK as a contributing factor, or all-cause death, or use of rescue therapy for HK at any time post-discharge up to 180 days.

- Population: FAS
- Endpoint: Time to first occurrence of either component of the composite outcome at any time post-discharge up to 180 days.
- Intercurrent event strategy: Participants who discontinue of treatment will continue to be followed up to the first component of the composite endpoint (treatment policy strategy). Rescue therapy for HK will be considered an event (composite variable strategy).

Participants who require ED visits without HK as a contributing factor will continue to be followed up to the first component of the composite endpoint (treatment policy strategy). Participants who die of any cause will be considered an event (composite variable strategy). Participants who are lost to follow-up will be censored at the date of loss to follow-up. Participants who have RAASI down-titration (including discontinuation) will continue to be followed up to the first component of the composite endpoint (treatment policy strategy).

- Population level summary (analysis): Kaplan-Meier plots of the survival function for the SZC and SoC treatment groups will be presented. Log-rank test for testing will be used to calculate a two-sided p-value, Cox proportional hazards ratio for estimation, with randomised treatment group as the independent variable. The HR and the two-sided 95% confidence interval will be presented. The risk difference and two-sided 95% confidence interval will be presented.

Sensitivity Analysis

- (i) Participants with all-cause hospital admissions will only be included where HK is a contributing factor.
- (ii) Participants who down-titrate RAASI (or discontinue) will be censored at the date of down-titration.

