- (iii) Providing there are sufficient events within each covariate (> 5 events) to support the analysis, the analyses of time-to-event secondary endpoints will be repeated in the FAS using an alternative population level summary where the Cox proportional hazards model will include randomised treatment group and the following baseline variables: age (as a spline), sex, presence of heart failure, diabetes, RAASI use, CKD stage and baseline K^+ (mild HK defined by K^+ between > 5.0 and ≤ 5.5 mmol/L and moderate/severe HK defined by K^+ between > 5.5 and ≤ 6.5 mmol/L) as independent variables.
- (iv) Additionally, the analysis will be repeated with the PPS analysis population. An additional sensitivity analysis will be conducted where participants who are lost to follow-up will be accounted for using an inverse probability weighting approach where similar participants who were not lost to follow-up will be re-weighted (hypothetical strategy). Full details regarding sensitivity analyses will be described in the SAP.

Subgroup analyses will be performed of the primary endpoint and of the main secondary endpoint, eg, by age, sex, presence of heart failure, diabetes, RAASI use, CKD stage, and baseline K^+ (mild HK defined by K^+ between > 5.0 and ≤ 5.5 mmol/L and moderate/severe HK defined by K^+ between > 5.5 and ≤ 6.5 mmol/L) at baseline, and by duration of hospitalisation. Additional participant subgroups may be considered, and further details on these analyses will be provided in the SAP.

2. Time to first occurrence of any component of all-cause hospital admission, or ED visit with HK as a contributing factor at any time post-discharge up to 180 days.

- Population: FAS
- Endpoint: Time to first occurrence of either component of the composite outcome at any time post-discharge up to 180 days.
- Intercurrent event strategy: Participants who discontinue treatment or who have ED visit without HK as a contributing factor will continue to be followed up to the first component of the composite endpoint (treatment policy strategy). Participants who die of any cause, use rescue therapy for HK or are lost to follow-up will be censored at the date of death, use of rescue therapy or loss to follow-up, respectively. Participants who have RAASI down-titration (including discontinuation) will continue to be followed up to the first component of the composite endpoint (treatment policy strategy).

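### The IPW sensitivity analysis for loss to follow-up drops lost participants instead of weighting their observed follow-up, can shift the hazard ratio when loss differs by arm, and names no variance estimator

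*SAP*

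**What the plan says.** Protocol 9.4.3.2 plans a sensitivity analysis of the main secondary endpoint in which losses are "accounted for using an inverse probability weighting approach where similar participants who were not lost to follow-up will be re-weighted", and leaves the details to the SAP.

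SAP 4.2.3.5 gives those details. A logistic model is fitted to a single indicator per participant (lost or not, with no date) on treatment and baseline covariates. The weight is the reciprocal of the predicted value, with no stabilising or scaling. Then: "The Cox proportional hazards model will then be conducted on participants not lost to follow-up". The same sentence refers back to the intercurrent-event rules of 4.2.3.1, under which losses are censored at the date of loss. No variance method is stated for this model. A bootstrap is specified for the risk difference (4.2.3.2) and in the mean cumulative count code (7.2).

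The main analysis works differently. Every FAS participant stays in, time runs to the earliest of event, loss or Day 180 (4.2.3.2), and losses are censored (4.2.3.3).

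SAP 4.2.4.5, 4.2.6.5, 4.2.7.5, 4.2.9.5, 4.2.10.5, 4.2.11.5 and 4.2.12.5 reuse 4.2.3.5.

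**The concern.** Weighting for censoring should let people still under observation stand in for similar people who have gone, from the moment they go. Here the lost are removed from Day 1, so whether a participant is analysed depends on something that happens later.

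Protocol 7.3 judges loss by whether contact exists when the study is completed. A participant can therefore be admitted on Day 30 and be classed as lost afterwards. Read literally, that event leaves the analysis. The reference to 4.2.3.1 does not settle the matter, because once lost participants are excluded nobody remains to be censored at loss.

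The weights cannot repair this. They depend on treatment and baseline covariates only, so they cannot correct for selection on whether an event occurred. An analysis meant to test robustness to loss could then disagree with the main result because of its own construction, or agree with it by accident. With the variance left open, its interval could also look more precise than the full-data interval.

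**Working it through.** **Inputs.** From Protocol 9.2.2: "Hazard ratio (HR; SZC/SoC): 0.329"; "Arm A (SZC): 83% (17% with the outcome/event of interest"; "Arm B (SoC): 56.8% (43.2% with the outcome/event of interest"; power 80%, alpha 5%, 20% drop-out after randomisation. The two-sided test is from Protocol 9.4.3.2 and the 1:1 allocation from 4.1.

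**The plan's own sample size.**
- HR: ln(0.83)/ln(0.568) = 0.329.
- Freedman events: (1.960 + 0.842)² × (1.329/0.671)² = 7.85 × 3.92 = 30.8, so 31.
- Mean event share: (0.17 + 0.432)/2 = 0.301. Then 31/0.301 = 103.0, so 52 per arm (104).
- 104/0.8 = 130 randomised; 130/0.8 = 162.5, so 163 enrolled.

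These agree with the Protocol. The documents give no figure for the IPW analysis, so it was simulated: 130 randomised, exponential event times at the planned rates, about 20% lost at uniform times, logistic weights, 1,500 to 2,000 runs per scenario.

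**Data discarded, loss unrelated to covariates.**
- Participants: 0.2 × 130 = 26.
- Literal reading: events fall from 35.7 to 31.5, a loss of 4.2 (4.2/35.7 = 12%).
- Lost only if before an event: no event goes, but about 22 event-free people do. The crude event share becomes 35.7/(130 − 22) = 33%, against a planned 30%.

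**Shift in the HR, true HR 1, 43.2% event risk in both arms (loss patterns assumed).** A weight that is constant within an arm leaves the within-arm event share unchanged, so the retained shares show the distortion.

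*Literal reading.* Suppose 40% (SoC) and 20% (SZC) of participants with an event are lost afterwards. A 10% background loss in each arm, unrelated to events, cancels.
- SoC: 0.432 × 0.6 = 0.259; 0.259/(0.259 + 0.568) = 0.313.
- SZC: 0.432 × 0.8 = 0.346; 0.346/(0.346 + 0.568) = 0.378.
- HR ≈ ln(1 − 0.378)/ln(1 − 0.313) = 0.475/0.376 = 1.26.

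Simulation gives 1.26 to 1.27, and 0.79 with the arms swapped. Coverage is only about 90% even with a robust variance.

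*Lost only if before an event.* Suppose loss hazards correspond to 30% (SoC) and 10% (SZC) over 180 days, unrelated to events. On a 180-day scale the event hazard is −ln(0.568) = 0.566, and the loss hazards are 0.357 and 0.105.
- SoC: event before loss = 0.566/(0.566 + 0.357) × (1 − 0.568 × 0.7) = 0.369; event-free and kept = 0.398; share = 0.482.
- SZC: 0.566/(0.566 + 0.105) × (1 − 0.568 × 0.9) = 0.412; event-free and kept = 0.511; share = 0.446.
- HR ≈ ln(1 − 0.446)/ln(1 − 0.482) = 0.591/0.657 = 0.90.

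Simulation gives 0.88 to 0.89. The ordinary Cox model with censoring at loss stays at about 1.0 in both cases.

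**Variance.** Raw weights average about 1/0.8 = 1.25, so 104 people count as 130 and 31.5 events count as 31.5 × 1.25 = 39.4, more than were observed in the whole FAS. A model-based SE should then be about √0.8 = 0.89 of the truth. Simulated results on the literal reading:

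| Quantity | Result |
|---|---|
| Model-based SE, design HR, loss unrelated to covariates | 0.368 |
| True SD, same setting | 0.421 |
| Model-based SE, Cox on the full FAS | 0.386 |
| 95% CI coverage over scenarios, model-based, raw weights | 90.8–92.8% |
| Coverage, model-based, weights scaled to mean 1 | 94.4–96.1% |
| Coverage, sandwich variance, raw weights | 94.2–96.4% |

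On the other reading (18-coefficient weight model, loss related to covariates), the model-based SE is 0.339 against an SD of 0.395. With less loss the expected ratio is √0.9 = 0.95 at 10% and √0.95 = 0.97 at 5%.

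**The case against.** Much of the case on the other side stands.

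- **A reader might infer that the SAP's intervals will be too narrow.** The SAP does not say so. It names neither a model-based nor a robust variance, and a sandwich variance or scaled weights bring coverage to about 95%.
- **A reader might infer that events before loss are certainly thrown away.** That is the literal reading, but the SAP does not say it outright. Under 4.2.3.1 and 4.2.3.2 a Day 30 admission fixes time and status before a later loss, so a programmer could decline to code that person as lost.
- **A reader might take 20% as the expected loss.** It is the planning figure for all drop-out after randomisation. Protocol 7.3 records withdrawal of consent separately, so 20% is an upper bound for loss to follow-up.
- **A reader might infer that nothing else addresses loss.** The reverse Kaplan-Meier plot (SAP 4.2.3.4) describes censoring by arm. The covariate-adjusted Cox model (4.2.3.5, if events suffice) keeps the FAS and uses the same baseline covariates.

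It can also be said that two clarifying sentences would do: define lost as lost before an event, and name a robust variance. They would save the events and the intervals. They would not remove the selection, because deleting only event-free people still moved a true HR of 1 to about 0.88.

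**Conclusion.** The point holds for the analysis population and the weighting; on variance it is an omission. As written, the analysis discards all follow-up of lost participants: at most about 26 of 130 people and, on the literal reading, 12% of events. Each reading is open to a different pattern. Loss after an event that differs by arm gave an HR of about 1.27 on the literal reading. Loss before an event that differs by arm gave about 0.88 on the other. Both patterns are assumptions chosen to show the mechanism and do not forecast this trial. With equal loss unrelated to events, the cost is mainly precision: the SD of the log HR is 0.421 against 0.394 for the full FAS on the literal reading. Narrow intervals follow only if model-based errors are combined with the raw weights.

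The figures assume constant hazards and 20% loss; the main simulation also takes uniform loss times and omits the country term from the Cox model. Only sensitivity analyses are affected. The log-rank test, the main Cox model and the testing order in SAP 3.3.4 are untouched.

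**What to change.** Amend SAP 4.2.3.5 before database lock:

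1. Keep all FAS participants in the weighted Cox model until event or censoring.
2. Count a participant as lost only if the loss precedes the event.
3. Replace the single weight with stabilised, time-dependent inverse-probability-of-censoring weights from the same baseline covariates, and state how the list is reduced if losses are too few.
4. Name a sandwich or bootstrap variance. If bootstrap, re-estimate the weights in each sample.

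The change carries to every endpoint that refers to 4.2.3.5. It costs SAP wording and a little programming, and needs no new data. The downside is possible weight instability: with at most about 22 to 26 losses, a model with an age spline, country and CKD stage may be too large. Reporting the weight distribution would show this.
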